The first exploratory objective of the Stage 2 study is to determine the pro-kinetic effect of repeated oral doses of ENT-01 on colonic motility as determined by Sitzmarks capsule retention. The Sitzmarks test will be performed on days 1-5 of the two-week run-in period and again at the end of the randomized treatment period.

The exploratory objectives will be to collect information on the effect of orally administered ENT-01 on sleep, temperature, memory, energy and mood in patients with Parkinson's disease. During the study, all patients will maintain a daily sleep diary. They will record bed time, sleep time and morning waking, hours slept each night, number and duration of wakes, and leg twitching/thrashing during the night. In addition, we will evaluate sleep indirectly using an I-Button which measures skin temperature. Diurnal variations in temperature correlate well with the sleep-wake cycle (Sarabia et al., 2008; van Marken Lichtenbelt et al., 2006). The patients will be asked to wear the I-Button attached to a wrist-band for five consecutive 24 hour periods during the baseline period (Period 3.1), during the stable-dose period (Period 3.2), the randomized period (Period 4) and part of the wash-out period. They will remove it only during showering. Mood, fatigue, hallucinations, memory and executive function will all be assessed at baseline, during the fixed dose period and at the end of the randomization period using the Beck Depression Index (BDI), REM behavior disorder questionnaire (RBDQ), Parkinson Fatigue Scale (PFS-16), University Miami Parkinson Disease Hallucination Questionnaire (UM-PDHQ), NMS questionnaire (NMS), MMSE and Trail-making A and B), respectively.

Primary Efficacy End-point:

The primary efficacy end-point will be regularization of bowel function as determined by stool frequency. This will be defined as an increase in frequency by one or more spontaneous, complete bowel movement per week compared to baseline or three or more spontaneous, complete bowel movements per week. Assessment will occur at the end of the fixed-dose period (Period 3.2) and baseline will be obtained at the end of the run-in period (Period 3.1) and all patients (n=40) will be compared with their baseline bowel function. During the randomized period (Period 4) the treatment group will be compared to the placebo group using the same criteria (n=20 in each group).

Summary of success criteria: (at least one of the following is met)

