PK subjects will come to the site on Day 1 of randomization ON AN EMPTY STOMACH and return their unused study drug at that time point. They will receive the first dose of medication at the site following the first PK blood draw, and complete the questionnaires listed below. PKs will also be performed at 1, 2, 4, and 8 hours post-dose. A sample for liver function tests will be drawn with the 8-hour post-dose PK draw. They will receive 4 daily doses to take home, then return on Day 6 to receive their 6th dose at the site after their first PK draw of the day. PKs will again be obtained post-dose at 1, 2, 4 and 8 hours, a sample for liver function tests will be drawn with the 8-hour post-dose PK draw, and all the questionnaires completed.

Following the 5-7 day course on the pro-kinetic dose, ALL patients will be randomized to drug or placebo and enter Period 4. Randomization will be 1:1 to treatment vs. placebo. Randomization will occur in accordance with the randomization schedule generated by [name] at Weill-Cornell Medical College. Patients and study staff will be blinded to actual study treatment and will remain blinded throughout the remainder of the study. BDI, MMSE, Trail making A and B, NMSQ, UM-PDHQ, PFS-16, RBDQ, PDSS, PAC-SYM and PAC-QOL will be administered prior to randomization. The UPDRS will be administered and weight and vital signs will be taken).

Assuming randomization is to treatment group, the patient will remain on that dose daily for a 6 day period (6 dosing days). Patients randomized to placebo will be switched to the same number of placebo tablets as they were taking prior to switching. All patients will continue to keep daily diaries during this period. The use of rescue medication (suppositories and enemas) for constipation will be permitted as needed if a bowel movement has not occurred for 3 days and recorded in the diary. Patients will be contacted daily. The suppository will be taken on the evening of the third day as shown in Figure 1 above. *Any bowel movement produced as a result of rescue medication will not be counted.*

Patients reaching their tolerability limit at a dose lower than a clinically effective dose (STDE) will be terminated from the study. We have included 40 patients in this Stage to allow for 15% drop-outs for reasons including tolerability.

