Patients will wear the I-Button continuously throughout the randomized period except during bathing periods. Stool and sleep diaries will be completed daily throughout the period. BDI, MMSE, Trail making A and B, NMSQ, UM-PDHQ, PFS-16, RBDQ, PDSS, PAC-SYM and PAC-QOL will be administered on the first (Visit 3) and last day (Visit 4).

Pharmacodynamics WSW:

On Day 6 of this randomized period, patients will have a second set of motility tests (Sitzmarks capsules) to determine whether there has been any improvement in colonic motility. Patients will be compared against their own baseline motility and the placebo group will also be compared to the treatment group. The protocol will be identical to the baseline motility assessment. Patients will self-administer one capsule per day for three days beginning on Day 3 of the randomization period with subsequent capsules taken on Day 4 and Day 5. An abdominal XR will be scheduled on Day 6. Motility at the end of the randomized period will be compared with

baseline for all 40 patients and motility will also be compared between treatment and placebo groups (20 patients per group).

Safety and tolerability will be reassessed throughout the randomized treatment period. The study coordinator will call each patient at the end of each day and patients will be told to call the coordinator whenever they need to.

Summary of Stage 2, Period 4

Stage 2								6 daily	doses
PERIOD 4 Double	All cohorts,	Afte	After 4th		Randomized	PLA	CEBO		\Rightarrow
	N=40	dose at the	at the	1:1					
blinded,	IV-40	1.1		LS1	DEi				
randomized									

Pharmacokinetics and LFTs: On the randomization Day 1, 7 patients from the treatment group and 3 patients from the control group will undergo blood draws for PK analysis at pre-dose, 1, 2, 4 and 8 hours after a dose and LFTs will be obtained on the last blood draw. These same 10 patients will undergo repeat blood draws for PK analysis and LFTs during their visit to the clinical trial unit on randomization Day 6 for the abdominal x-ray and repeated patient questionnaires/surveys. Study medication will be administered by study staff on randomization Day 1 and again on Day 6 after the first blood draw.

PERIOD 5 (Stage 2): Wash-out period

Duration: 2 weeks

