9 STUDY PROCEDURES

9.1 Sitzmarks assessment of colonic motility in Stage 2

On Day 8 of the run-in period and again on Day 3 of the randomized period, patients will be reminded to self-administer a Sitzmarks capsule (contains 24 radiopaque markers; Konsyl Pharmaceuticals, Texas, USA). The patient will be instructed to abstain from using suppositories or enemas if possible until they return on Day 11 (or day 6 of randomized period). If they have to use suppositories on day 11 (or Day 6 of randomized period), make sure it's recorded in the daily diaries. An abdominal XR will be scheduled for Day 11 of run-in and Day 6 of randomized period.

On Day 11 of the run-in Period and again on Day 6 of the randomized period, an abdominal XR will be performed to determine the location and the extent of elimination of the radioisotope markers. Patients who expel at least 80% (19 or more of the markers) have grossly normal colonic transit. If remaining markers are scattered about the colon, the condition is most likely hypomotility or colonic inertia. If remaining markers are accumulated in the rectum or

rectosigmoid, the condition is most likely functional outlet delay. For patients whose markers accumulate in the rectosigmoid or when markers are retained diffusely, instruct patient to maximize liquid intake for the next two weeks.

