10.3.2 Efficacy Endpoints

Frequency of bowel movements:

The frequency of bowel movements will be determined via a daily diary where the passage of a bowel movement or absence thereof will be recorded daily throughout the study. *Bowel movements that are the consequence of a rescue medication or suppository will not be counted if they occur within 24 hours of the rescue medication or suppository.* Episodes of incontinence will also be recorded.

Success will be defined as an average complete spontaneous stool frequency increase by 1/week or more compared to baseline or 3 or more complete spontaneous stools/week. Baseline will be the run-in period weekly average and treatment period will be determined as the weekly average during the fixed dose (40 patients) treatment period.

Colonic Motility:

Colonic motility will be determined using the Sitzmarks technique at the beginning of the run-in period and again at the end of the randomized treatment period during Stage 2. The primary measure of interest is the mean colonic transit (MCT) time estimated with a single film (Metcalf et al., 1987).

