patients who were randomized to receive ENT-01 (between 17 and 20 patients). This analysis will consist only of those patients with assessments at baseline (end of run-in period, Period 3.1), the end of Period 4, and the end of Period 5. This analysis will have between 17 and 20 patients and will be done using an exact sign test of equality of paired proportions.

Exploratory analyses:

The first exploratory analysis will of the colonic motility values as measured by an estimate of the mean MCT times. Comparisons will be made within each patient at different time points (i.e. baseline and the end of fixed period) as well as between patient groups (i.e. values observed at the end of randomization period, period 4 for the placebo and the ENT-01 treated groups). The primary endpoint for this analysis is the MCT based on a single film estimate. From a previous study (Ashraf et al., 1997), and estimate for the average MCT for constipated patients with Parkinson's disease is 53.4 hours and an estimate of the standard deviation is 15.9 hours. A paired t-test will be used to compare the mean change in MCT at the end of the fixed period from baseline. A sample size of 34 (40) patients will have 80% power to detect a mean change of 11.1 hours (10.2 hours) with a 0.05 two-sided level of significance and using a paired t-test. This calculation assumed a conservative estimate of 22.4 hours for the standard deviation of the change in MCT, which is the square root of 2 times the variance of the baseline standard deviation. The comparison of the average MCT between the control group and the group randomized to ENT-01 at the end of the randomization period will be made with a two-group t-test.

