Exploratory analyses will also be done with respect to the sleep data, the body temperature data, mood, fatigue, hallucinations, overall NMS scale and all other questionnaires and neurocognitive tests. These parameters will be summarized numerically and graphically. There will also be comparisons done of changes over time within a patient (i.e. between baseline, end run-in period, and at the end of the fixed dose period, Period 3.2) and differences between groups (i.e. between patients in the Enterin arm and in the placebo arm at the end of period 4). As before, continuous measurements within a patient will be compared with a paired t-test (transforming the data if necessary) and continuous measurements between patient groups will be compared with a two-group t-test (transforming the data if necessary). In addition, these data will be analyzed using a mixed linear model since there are multiple measurements over time. Categorical data will be

compared with a chi-squared test or a Fisher's exact test if the expected cell counts are too small

for a chi-squared test.

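### Protocol 10.5 powers a paired colonic-transit test at a time when no film is taken, and the SAP omits the transit analyses without listing them as dropped

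*Protocol*

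**What the plan says.** **The test and its power.** Protocol 10.5 (Stage 2, exploratory analyses) specifies: "A paired t-test will be used to compare the mean change in MCT at the end of the fixed period from baseline". The power statement follows: "A sample size of 34 (40) patients will have 80% power to detect a mean change of 11.1 hours (10.2 hours" in brackets for the larger number), two-sided 0.05, with an SD of change of 22.4 h. The same section sets this apart from a two-group comparison of MCT at the end of Period 4. Protocol 10.1.2 identifies the end of the fixed-dose period with the end of Period 3.2. So does the next paragraph of 10.5, on sleep and questionnaire data: "at the end of the fixed dose period, Period 3.2".

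**The films.** Protocol 9.1: "An abdominal XR will be scheduled for Day 11 of run-in and Day 6 of randomized period". Protocol 2.2 places the Sitzmarks test in the "two-week run-in period and again at the end of the randomized treatment period", and 10.3.2 agrees: "again at the end of the randomized treatment period during Stage 2". The exploratory endpoints in 2.2 are likewise defined over the randomized period against baseline. The Stage 2 schedule in Appendix 2 has no X-ray in Period 3.2.

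**Treatment at the second film.** Allocation in Period 4 is 1:1. Section 3.1: "Patients randomized to placebo will be switched to the same number of placebo tablets as they were taking prior to switching". The same section compares motility at the end of that period with "baseline for all 40 patients and motility will also be compared between treatment and placebo groups (20 patients per group").

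**The SAP.** Section 1 says that it supersedes the protocol's statistical considerations. MCT appears only in the abbreviation list. It is absent from the objectives (3.2.2), the PD analyses (7.7.1, 7.7.2) and the listings (7.9). Section 5.1 reports no changes from the protocol's planned analyses. Sections 1 and 9 name two dropped analyses, both on the Success endpoint.

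**The concern.** Colonic motility is the first exploratory objective of Stage 2. A reader of 10.5 would take it that an on-drug change of about 11 h can be detected with 80% power in 34 patients. That needs a film while all of them are on drug, and the schedule has none. At the film that is taken, a within-patient comparison either covers about half the patients (those still on ENT-01) or mixes patients on and off drug.

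The SAP adds a second difficulty. A prespecified test with its own power statement is no longer in the plan, and the sections meant to record such changes do not mention it. The SAP does say what happens to other exploratory measures that it leaves unanalysed: Trail Making and PDSS in 4.4.3.10, and the I-Button in 7.8.8. A reader of the final report could not tell from the SAP why the transit results are missing.

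**Working it through.** **Inputs.** From Protocol 10.5: baseline SD 15.9 h, SD of change 22.4 h, two-sided 0.05, n = 34 (40), change d = 11.1 h (10.2 h). From Protocol 10.5 and section 3.1: 17 to 20 patients per arm. Two quantities are not given and are varied as assumptions: the within-patient correlation r, and the share f of the drug effect that patients switched to placebo still show on Day 6.

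**Step 1: reproduce the plan's figure.** Paired t-test power from the noncentral t distribution, df = n − 1, noncentrality = (d / SD) × √n.
- n = 34: (11.1 / 22.4) × √34 = 2.89, power 80.1%. The change detectable with 80% power is 11.09 h.
- n = 40: (10.2 / 22.4) × √40 = 2.88, power 80.2%. Detectable change 10.18 h.
- SD of change: √2 × 15.9 = 22.49 h, stated as 22.4 h. This corresponds to r = 0.

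The stated figures are right for their inputs. The fault is the timepoint.

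**Step 2: patients still on ENT-01 at the Day 6 film.** Same formula with n = 17 (20). For r > 0, SD of change = 15.9 × √(2(1 − r)), assuming the same SD at both films. At r = 0 the protocol's 22.4 h is used; the noncentrality is (11.1 / 22.4) × √17 = 2.04 and (10.2 / 22.4) × √20 = 2.04.

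| Assumed r | SD of change (h) | Detectable change, n = 17 (20) | Power at 11.1 h (10.2 h) |
|---|---|---|---|
| 0 | 22.4 | 16.2 h (14.8 h) | 48% (49%) |
| 0.3 | 18.8 | 13.6 h (12.4 h) | 63% (63%) |
| 0.5 | 15.9 | 11.5 h (10.5 h) | 77% (78%) |
| 0.7 | 12.3 | 8.9 h (8.1 h) | 94% (94%) |

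**Step 3: all patients pooled at the Day 6 film, as in section 3.1.** Half the patients shift by d and half by f × d, so the mean change is d(1 + f)/2. With f = 0 and d = 11.1 h that is 5.55 h. Simulated one-sample t-test, power at 11.1 h for n = 34 (10.2 h for n = 40):

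| Effect kept on placebo, f | SD 22.4 h | SD 15.9 h (r = 0.5) |
|---|---|---|
| 0% | 27% (27%) | 46% (47%) |
| 25% | 40% (41%) | 67% (67%) |
| 50% | 55% (55%) | 83% (83%) |
| 75% | 69% (69%) | 93% (93%) |
| 100% | 80% (80%) | 98% (98%) |

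At the protocol's own SD, the pooled test reaches 80% only if switching to placebo loses none of the effect.

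**Step 4: SAP against protocol.** Protocol 10.5 has two MCT analyses, one within patients and one between arms. SAP 7.7 rules out formal arm comparisons for PD variables in the randomized population, which could be read to cover the second. It does not reach the first, and MCT is not among the SAP's PD variables. SAP Table 3 (27 July 2017 schedule) has capsule and X-ray rows; Table 4 (02 February 2018 schedule) has neither. SAP 2.1 nevertheless says that the amendment changed only the dose range and removed the randomization period.

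**The case against.** The strongest reply is that 10.5 contains one misplaced phrase. Protocol 2.2, 3.1, 9.1, 10.3.2 and Appendix 2 agree on the Day 6 film, and 2.2 already defines the within-patient endpoint over the randomized period. The planned between-arm test does match that film. This stands, and it is why the repair is to align 10.5 with those sections. It does not rescue the power statement, which was computed for 34 (40) patients on drug.

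A reader might infer that no film could give the claimed power. The documents do not support that. The 48% (49%) rests on an SD that the protocol itself calls conservative. With r = 0.7 the ENT-01 patients alone exceed 80%. With r = 0.5 the pooled test does so if placebo patients keep half the effect. Neither quantity is given.

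A reader might also take a paired test in the ENT-01 arm alone to be the intended analysis. Neither document plans one for MCT. The figures for that arm show what the film can say about change on drug; they do not replace the planned test.

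Finally, it can be said that the amendment makes the matter moot, and that SAP 5.1 is already contradicted by SAP sections 1 and 9. Removal of the randomized period does probably explain the omission. But the 02 February 2018 protocol was not supplied, so whether it formally withdrew motility cannot be checked. Inferring selective reporting would go too far: Table 4 and SAP 3.2.2 are both consistent with a formal withdrawal. What remains is that the SAP does not say so.

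**Conclusion.** The point holds in two parts. First, the 80% power in Protocol 10.5 for an on-drug change of 11.1 h (10.2 h) belongs to a measurement that the 27 July 2017 design does not take. At the protocol's SD, the patients still on ENT-01 at the only post-baseline film could detect a change about 1.5 times as large (16.2 / 11.1 = 1.46; 14.8 / 10.2 = 1.45). The size of the shortfall depends on the unstated within-patient correlation and, for the pooled comparison, on carryover after the switch to placebo; under favourable assumptions it disappears. The sample sizes are those planned in July 2017, and the detectable change is larger if fewer patients were filmed on drug.

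Second, the SAP omits both MCT analyses, while section 5.1 reports no changes and section 9 does not name them.

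The analysis is exploratory. Nothing here touches the primary endpoint or its power.

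**What to change.** 1. **Protocol 10.5.** Set the within-patient timepoint to the Period 4 Day 6 film, consistent with 2.2 and 3.1, and remove the claim of 80% power for 11.1 h (10.2 h) on drug. State instead that, under the 27 July 2017 design and at SD 22.4 h, the 17 (20) patients still on ENT-01 could detect 16.2 h (14.8 h), with 48% (49%) power at the former values. Add that these figures depend on a within-patient correlation that is not given (at r = 0.5, 11.5 h (10.5 h) and 77% (78%) power; at r = 0.7, 94% power). Add that the all-40 comparison in 3.1 mixes arms, so that its power runs from 27% to 80% at SD 22.4 h, and from about 46% to 98% at r = 0.5, as the effect kept on placebo goes from none to all.
2. **SAP 5.1 and 9.** Name the within-patient and between-arm MCT analyses as not performed and give the actual reason. Loss of the period that held the only post-baseline film is the likely one, to be confirmed against the 02 February 2018 protocol.
3. **Alternative to item 2.** Add to SAP 7.7.1 a descriptive summary of MCT change by arm, with 95% confidence intervals and the actual n, for patients filmed under the 27 July 2017 protocol. Include no between-arm test, in line with SAP 7.7.

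The cost is wording, plus one descriptive table if item 3 is chosen. No procedure is added. The stated sensitivity of the motility analysis becomes less favourable, or its omission is stated openly.

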11 ESTIMATED DURATION OF THE STUDY

This study has an estimated duration of 8 weeks for each patient during each stage.

Maximum dosing days for each patient will be no more than 8 days during Stage 1 and 25 days

during Stage 2. The study duration from first patient in to last patient out is expected to be 9-12

months.

12 ADMINISTRATIVE PROCEDURES AND ETHICAL CONSIDERATIONS

12.1 Medical Care

This study has an estimated duration of 21 weeks. During this period, patients will be on

medication for a maximum of eight weeks. None of the patients will be given medication during

the run-in period or the wash-out period.

12.2 Patient Information and Informed Consent

The Principal Investigator(s) at each center will ensure that the patient is given full and

adequate oral and written information about the nature, purpose, possible risk and benefit of the

study. Patients must also be notified that they are free to discontinue from the study at any time.

The patient should be given the opportunity to ask questions and allowed time to consider the

information provided.

The patient's signed and dated informed consent must be obtained before conducting any

study procedures.

The Principal Investigator(s) must maintain the original, signed Informed Consent Form.

A copy of the signed Informed Consent Form must be given to the patient.

12.3 Study Monitoring

Before an investigational site can enter a patient into the study, a representative of Enterin, Inc.

will visit the investigational study site to:

• Determine the adequacy of the facilities

CP1001 v0.9, Version Date: 27JUL2017

64

• Discuss with the investigator(s) and other personnel their responsibilities with regard to protocol adherence, and the responsibilities of Enterin, Inc. or its representatives. This will be documented in a Clinical Study Agreement between Enterin, Inc. and the investigator.

During the study, a monitor from Enterin, Inc. or representative will have regular contacts with the investigational site, for the following:

- Provide information and support to the investigator(s)
- Confirm that facilities remain acceptable
- Confirm that the investigational team is adhering to the protocol, that data are being
 accurately recorded in the case report forms, and that investigational product accountability
 checks are being performed
- Perform source data verification. This includes a comparison of the data in the case report
 forms with the patient's medical records at the hospital or practice, and other records
 relevant to the study. This will require direct access to all original records for each patient
 (e.g. clinic charts).
- Record and report any protocol deviations not previously sent to Enterin, Inc.
- Confirm AEs and SAEs have been properly documented on CRFs and confirm any SAEs have been forwarded to Enterin, Inc. and those SAEs that met criteria for reporting have been forwarded to the IRB.

The monitor will be available between visits if the investigator(s) or other staff needs information or advice.

